**2) Objectives**

Aim:

- Determine if external fixation decreases soft tissue complications compared to splinting.
- Determine if external fixation decreases time to definitive surgical stabilization and improves final fixation compared to splinting.
- Determine if external fixation improves functional outcomes as evaluated by validated functional scoring systems.

Hypothesis:

- External fixation improves definitive fixation and functional outcomes of acute calcaneal fractures with decreased complication rates compared to splinting

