### **III. Outcomes**

#### **Primary outcome**

1. Time to definitive surgery
2. Soft tissue complications (at routine follow ups which are 2, 6, & 12 weeks, and 6, 12, & 24 months after surgery)

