#### **Secondary outcomes**

1. Union rate via standard weight bearing plain radiographs ( harris axial/lateral views) at 6 weeks, 12 weeks, 6 months, 1 year, and 2 years after surgery. We will also obtain a 1X CT scan of the injured foot at 1 year after surgery to monitor for arthritic progression.
2. Radiographic parameters(Bohler's angle, clancaneal height/width/length, and angle of Gissan)
3. Other complications
4. Clinical outcomes will be evaluated to monitor patients' activity levels, pain, and functional status. This will be done primarily using the web-based Surgical Outcome System™ (SOS)
  - The SOS is currently a UCD IRB approved study (IRB # 1192222). It is a large international web-based registry that permits collection of baseline characteristics of patients undergoing orthopedic procedures. The data is collected using direct entry into a web-based collection system called the Surgical Outcome System (SOS). By completing these surveys, the investigator surgeon has the opportunity to monitor the subjects progress after treatment, even when they are not scheduled to see the provider. The investigator surgeon will also be able compare the outcomes to the average de-identified global data.
  - In order to utilize the web-based surveys, we would invite patients to dual enroll and consent into SOS. If, the subject forgoes SOS participation, the surveys may be filled out manually and this data will not be part of SOS.
  - Subjects fill out surveys before visits at 7 total time points: preoperatively, & postoperatively at 2, 6, and 12 weeks and 6 months, 1 and 2

**PROTOCOL TITLE:** Staged External Fixation of Acute Calcaneal Fractures

years. The surveys may include the Visual Analogue pain score(VAS), Patient-reported outcomes measurement information system 10 short form (PROMIS 10), or Veterans RAND 12 item Health survey (VR-12), Foot function index questionnaire (FFI-R) or Foot and Ankle Ability measure activities of daily living (FAAM ADL), and FAAM sport

**IV. Analysis:** The data will be analyzed for differences between splinting and external fixator treatment groups. Data will be stratified and analyzed for further differences in outcomes based on other factors (ie: demographics, comorbidities..)

- To assess significance the alpha level will be set at <0.05.
- Continuous data will be reported as means, standard deviation(SD), range, with 95% confidence intervals

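### The hypothesis and the primary outcomes match only in part, and the secondary outcomes that carry fixation and function have no lead measure, lead visit or multiplicity rule

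*Combined protocol and SAP*

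**What the plan says.** Section 2 (Objectives) lists three aims: fewer soft tissue complications; shorter time to definitive stabilization together with better final fixation; and better function on validated scores. It then gives one hypothesis: "External fixation improves definitive fixation and functional outcomes of acute calcaneal fractures with decreased complication rates compared to splinting".

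Section 6.III names two primary outcomes. The first is "Time to definitive surgery". The second is "Soft tissue complications (at routine follow ups which are 2, 6, & 12 weeks, and 6, 12, & 24 months after surgery").

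The secondary outcomes are:

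- union, read "at 6 weeks, 12 weeks, 6 months, 1 year, and 2 years after surgery";
- "Radiographic parameters(Bohler's angle, clancaneal height/width/length, and angle of Gissan"), with no visit stated;
- "Other complications", not defined further;
- patient-reported scores, of which the plan says "Subjects fill out surveys before visits at 7 total time points: preoperatively, & postoperatively at 2, 6, and 12 weeks and 6 months, 1 and 2" years. The instruments are given as possibilities, two of them as either/or pairs: VAS pain; PROMIS 10 or VR-12; FFI-R or FAAM ADL; and FAAM sport.

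Section 6.IV gives one significance rule: "To assess significance the alpha level will be set at <0.05". It also promises further stratified analyses, and descriptive summaries with 95% confidence intervals. Section 6.I says that multiple comparisons were considered when 35 per group was chosen, but names no method, outcome or number of comparisons.

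**The concern.** Two of the three parts of the hypothesis, and all or part of two of the three aims, rest on outcomes with no prespecified test. The plan does not call these outcomes exploratory, so a reader may fairly expect a verdict on them. It does not say which score, at which visit, would show better function, or which radiographic measure, at which visit, would show better fixation. Nor does it say whether the parts of the hypothesis stand or fall together.

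With interchangeable instruments and six postoperative visits, a claim of better function could rest on whichever comparison fell below 0.05. Meanwhile the outcome listed first as primary has no place in the hypothesis, so a clear result on it would leave the hypothesis undecided.

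**Working it through.** **The plan's own figure.** The plan states no number of tests. The only figure linked to multiplicity is the sample size. The dropout step reproduces: 70/(1 − 0.30) = 100, or 50 per group. The base of 35 per group cannot be traced, because no effect size, standard deviation or event rate is given. Any multiplicity allowance inside it is therefore not visible, and alpha stays at 0.05.

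**Where each element sits.**

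| Element | Aims | Hypothesis | Outcome level |
|---|---|---|---|
| Soft tissue complications | Aim 1 | Yes, as complication rates | Primary |
| Time to surgery | Aim 2 | No | Primary |
| Fixation | Aim 2 | Yes | Secondary |
| Function | Aim 3 | Yes | Secondary |

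**Possible function comparisons.** Taking one of each either/or pair gives 4 scores; using all gives 6. With 6 postoperative visits this is 4 × 6 = 24 or 6 × 6 = 36. Testing every score at every visit is an assumption, as is counting pain and general-health scores as function. A narrower count takes only FFI-R or FAAM ADL, plus FAAM sport: 2 × 6 = 12.

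**Chance of a favourable result on function.** Assume no true difference, two-sided tests at 0.05 and a common correlation ρ between the k test statistics. One test favours external fixation by chance with probability 0.05/2 = 2.5%. For k tests,

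P(at least one z > 1.96) = 1 − ∫ φ(c) · Φ((1.96 − √ρ·c)/√(1 − ρ))^k dc.

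For ρ = 0 this reduces to 1 − 0.975^k. Numerical integration gives:

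| k | ρ = 0 | ρ = 0.3 | ρ = 0.5 | ρ = 0.7 | ρ = 0.9 |
|---|---|---|---|---|---|
| 1 | 2.5% | 2.5% | 2.5% | 2.5% | 2.5% |
| 12 | 26.2% | 20.2% | 16.0% | 11.6% | 6.7% |
| 24 | 45.5% | 31.1% | 23.0% | 15.6% | 8.1% |
| 36 | 59.8% | 38.4% | 27.6% | 18.1% | 9.0% |

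The documents give no correlations. For 0.7 to 0.3, with 24 to 36 tests, the range is about 16% to 38%.

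**Chance of meeting several parts together.** Take fixation as 5 radiographic measures at one visit plus union at 5 visits, so k = 10. The same formula gives 10.7% (ρ = 0.7) to 17.8% (ρ = 0.3). Treating fixation and function as independent of each other:

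- lowest (24 function tests, ρ = 0.7): 0.156 × 0.107 ≈ 1.7%;
- highest (36 function tests, ρ = 0.3): 0.384 × 0.178 ≈ 6.8%.

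If one independent test must also show fewer complications, multiply by 0.025: about 0.04% to 0.17%. Even with every test independent, simulation puts this at no more than about 0.3%.

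**The case against.** The strongest reply is that the hypothesis is a directional conjunction that includes a primary outcome. It asks for better fixation, better function and fewer complications, and soft tissue complications are both primary and the first aim. This stands.

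A reader might infer that any one of dozens of secondary tests could confirm the hypothesis while the primary outcomes fail. The documents do not support that. It needs the complications clause to be ignored, or to be read as covering only the undefined other complications. The chance of any hit, in either direction, among 34 to 46 pooled tests (24 or 36 function tests plus 10) would be large, but it describes a different event: half of those hits would favour splinting, and a hit in one domain does not meet the others.

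Three further replies carry weight:

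- Time to surgery is not missing from the objectives. It is in the second aim, just above the hypothesis that omits it.
- The number of tests is inferred. The plan does not say that each score is tested at each visit.
- Descriptive reporting with confidence intervals is already planned.

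The reference to multiple comparisons in section 6.I carries less weight. It is unspecified and does not reach the analysis section. None of these replies supplies a lead measure, a lead visit or a rule for judging the function and fixation aims, each of which can be claimed separately.

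**Conclusion.** The concern holds as a partial mismatch and a gap in prespecification. The hypothesis and the primary outcomes share only complications. Time to surgery is primary but absent from the hypothesis, while fixation and function are in the hypothesis but only secondary.

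A claim of better function alone could arise by chance about 16% to 38% of the time, against a nominal 2.5%. This assumes 24 to 36 tests, a separate test at each visit, two-sided testing and common correlations of 0.7 to 0.3. It falls to about 8% to 9% at a correlation of 0.9, and to about 12% to 20% if only two foot-specific scores are counted at correlations of 0.7 to 0.3. The three-part hypothesis read as a whole is well protected, so these figures should not be presented as its false-positive rate. This is a cheap improvement, not a flaw that undermines the primary comparison.

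**What to change.** 1. In section 2, word the main hypothesis around the two primary outcomes, and state function and fixation as secondary hypotheses.

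2. In sections 6.III and 6.IV, name one functional test (for example FAAM ADL at 1 year) and one radiographic test (for example Bohler's angle at one stated visit), tested in that order. Open this sequence in one of two ways:
   - only after both primary outcomes are met, each at 0.05; or
   - after a primary outcome is met under a split alpha, such as 0.025 each, with only that alpha passed on.

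   Opening it after either primary outcome at an unadjusted 0.05 would not control error: with independent tests it opens falsely 1 − 0.95² = 9.75% of the time. The gate also needs a single stated test for each primary outcome, so soft tissue complications over the six visits should be reduced to one comparison.

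3. Report all other secondary comparisons as estimates with 95% confidence intervals and no claim of significance.

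The outcome list, visits and number of patients stay as they are, and the edits are short. The main cost is that fewer secondary results may be called significant. The split-alpha option also costs some power: for a continuous outcome with 35 per group and 80% power, the detectable standardized difference rises from (1.960 + 0.842) × √(2/35) = 0.67 to (2.241 + 0.842) × √(2/35) = 0.74. Requiring both primary outcomes avoids that, but the secondary tests are then reached less often.

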**3) Background**

Acute displaced calcaneal fractures are a regularly encountered orthopedic injury that can be complex to treat. Operative treatment of these fractures has been shown to have improved functional outcome scores compared to patients treated non-operatively. Operative treatment aims to reduce the articular surface and restore radiographic parameters such as Bohler's angle, both of which have been correlated with improved long term morbidity.

Within operative management options the definitive operative choice to minimize soft tissue and post-operative complications remains controversial. Minimally invasive and percutaneous fixation techniques of complex calcaneus fractures have been shown to decrease soft tissue complications compared to open reduction internal fixation (ORIF) techniques. However, there is concern about the use of percutaneous techniques leading to a loss of reduction and important radiographic parameters. Additionally, direct visualization that is offered in an open technique is often preferable.

## PROTOCOL TITLE: Staged External Fixation of Acute Calcaneal Fractures

Clinicians favoring an open technique have sought ways to minimize soft tissue complications by using a temporary external fixator as similar to the often utilized staged management of tibial plateau and tibial plafond fractures. This delay is necessary for soft tissue swelling to subside prior to surgery with the external fixator allowing for prevention of early clot and fibrinous material between malaligned fracture fragments that may impede definitive reduction in the operating room. Additionally, early temporary fixation will restore native soft tissue biology and calcaneal morphology allowing for optimal healing conditions prior to definitive fixation.

Given these benefits, external fixators have been studied to treat acute calcaneus fractures definitively, in a brief-(days) or prolonged- (months) staged approach. To date there has only been three case series describing a brief-staged technique with use of an external fixator for treatment of complex calcaneal fractures. Our study will provide the first prospective-randomized controlled trial of this potentially practice changing protocol. The purpose of this study is to compare the efficacy of temporary external fixation vs. splinting for the treatment of acute calcaneal fractures prior to definitive surgical fixation.

#### **4) Inclusion and Exclusion Criteria**

Inclusion Criteria	Exclusion Criteria

• Voluntary consent

• Age 18 to 69

• Clinical and/or advanced imaging confirming an acute calcaneal fracture that has occurred within 2 days of which, eventually definitive surgery is recommended/accepted.

	

• unable to consent

• age <18

• Prior surgery of the affected extremity

• Prisoners

• Pregnant women

• Inflammatory arthritis

• Non-english speaking spatients

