## 5) Study Timelines

- Study will begin after IRB approval
- Patient recruitment will take place over two years, however this may be longer depending on the number of patients who require definitive surgery
- The duration of the subject's participation in the study will conclude at two year postoperatively
- The primary analysis will be complete within 3 years of the study start time

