## 6) Study Endpoints and Procedures involved

### I. Design

- Subjects will be recruited from the UC Davis Medical Center. Adults diagnosed with an acute (<1-2 days from injury) calcaneal fracture recommended for operative treatment will be offered enrollment into the study.
- A total of 100 patients will be enrolled in the study. The sample size can be calculated at 35 per treatment groups after considering multiple comparisons and using an 80% power and an  $\alpha = 0.05$ . This would require a minimum of 70 patients for the study; however, factoring in a 30% dropout rate, a minimum of 100 patients will be enrolled into the study with a minimum of 50 patients per group.

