### II. Methods

- Patients will be randomized to one of two treatment groups: temporary external fixation or temporary splinting. Both temporary treatments are those routinely used/available at the UCD health system. Subjects are to wear the temporary treatment method until definitive surgery.
- Safety endpoints occur at conclusion of the definitive fixation of their calcaneal fracture.

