**15) Sharing of Results with Subjects**

Subjects will be aware of the survey scores as they are self-reported. Subjects will be aware of which treatment option they receive as they are visible. The results of this study will not be shared with other subjects or others.

**16) Prior Approvals:** IRB approval

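### Eligibility is not clearly fixed before randomisation, so the withdrawal rule could remove randomised patients who do not go on to surgery, possibly unequally by arm

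*Combined protocol and SAP*

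**What the plan says.** Section 4 (Inclusion and Exclusion Criteria) requires "Clinical and/or advanced imaging confirming an acute calcaneal fracture that has occurred within 2 days of which, eventually definitive surgery is recommended/accepted". It sets no time by which the recommendation or the acceptance must be made, and the slash leaves open whether one or both are needed.

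Section 6, I. Design, describes entry differently: a patient with an acute "calcaneal fracture recommended for operative treatment will be offered enrollment into the study". There the recommendation comes before the offer of enrolment. The patient's acceptance of surgery is not mentioned.

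Section 6, II. Methods, states that "Patients will be randomized to one of two treatment groups: temporary external fixation or temporary splinting" and that "Subjects are to wear the temporary treatment method until definitive surgery". It does not place randomisation relative to the surgical decision. Section 15 confirms that allocation is not concealed from patients: "Subjects will be aware of which treatment option they receive as they are visible".

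Three other places bear on the point:

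- Section 10 (Withdrawal of Subjects) lists ceasing to satisfy the study's requirements among the grounds for withdrawal.
- Section 6, III. Outcomes, makes time to definitive surgery one primary outcome. The other is soft tissue complications at visits timed from surgery.
- Section 6, IV. Analysis, says the two treatment groups will be compared. It defines no analysis population and gives no rule for a randomised patient who never has definitive surgery.

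**The concern.** Randomisation makes the arms comparable as randomised. That protection is lost if membership of the trial can be revised afterwards on grounds the treatment may influence. Here it could be influenced. The Background section gives the protocol's own rationale: early temporary fixation is expected to restore soft tissue and bone shape before definitive surgery. If the device changes skin and alignment, it may change whether a surgeon still recommends surgery. Because patients know which device they have, it may also change whether they still accept it.

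The wording alone does no harm. The risk comes from several rules acting together: an entry criterion with no time limit, a withdrawal ground that refers back to requirements, primary outcomes that have no defined value without surgery, and no analysis set that keeps everyone randomised. The comparison could then become one between patients in each arm who reached surgery, which are not necessarily comparable groups.

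**Working it through.** **Following one patient through the sections.** Take a patient for whom surgery is recommended on presentation, who is randomised and fitted with the device, and who later declines surgery.

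1. Under I. Design the patient was eligible, because the recommendation existed when enrolment was offered.
2. Under section 4 the answer is unclear. If recommendation is enough, the criterion was met. If acceptance is needed and may come later, it was never met.
3. Under section 10, on the second reading, the patient can be withdrawn for not satisfying requirements.
4. Under III. Outcomes, the patient has no time to surgery and no visit timed from surgery.
5. Under IV. Analysis, nothing requires the patient to be kept.

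The same trace applies if the surgeon revises the recommendation after allocation.

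**The plan's own figure.** I. Design gives 35 per group, 30% dropout and 100 enrolled. 70/(1 - 0.30) = 100 and 35/(1 - 0.30) = 50, so the inflation reproduces. The allowance is 50 - 35 = 15 patients per arm. Removing 10-20% of one arm is 5 to 10 of 50. That fits inside the allowance, so the evaluable target could still be met and the loss might attract no attention.

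**Illustration for complications.** All inputs are assumptions, because the documents give neither a complication rate nor a rate of not reaching surgery. Let the true rate be 25% in both arms, let a fraction f be removed from one arm only, and let r be the complication risk in those removed. The rate in those left is (0.25 - f × r)/(1 - f).

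| f | r | Calculation | Rate in those left | Shift from 25% |
|---|---|---|---|---|
| 0.10 | 0.05 | (0.25 - 0.005)/0.90 | 27.2% | +2.2 points |
| 0.20 | 0.05 | (0.25 - 0.010)/0.80 | 30.0% | +5.0 points |
| 0.10 | 0.50 | (0.25 - 0.050)/0.90 | 22.2% | -2.8 points |
| 0.20 | 0.50 | (0.25 - 0.100)/0.80 | 18.8% | -6.2 points |

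If r = 0.25, those left have a 25% rate whatever f is. If f and r are the same in both arms, the two rates move together and the difference stays zero.

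**Illustration for time to surgery.** As a worst case, assume a normal outcome and remove exactly the slowest fraction q of one arm. The mean of the rest falls by φ(z)/(1 - q) standard deviations, where z is the 1 - q quantile and φ the normal density:

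- q = 0.10: 0.1755/0.90 = 0.20 SD.
- q = 0.20: 0.2800/0.80 = 0.35 SD.

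For scale, 35 per group with 80% power at two-sided 0.05 detects √(2/35) × (1.960 + 0.842) = 0.67 SD. The protocol states neither an effect size nor sidedness, so 0.67 is itself a back-calculation under an assumption.

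**The case against.** The strongest reply is that *eventually* describes when the surgery takes place, not when it is decided. This is a trial of staged treatment, with a temporary device first and definitive surgery once swelling has settled. On that reading section 4 describes a patient who is now a candidate for later surgery, I. Design gives the working order (recommendation, then enrolment), and II. Methods expects every subject to receive operative treatment. This is a fair reading, and it stands. A reader might infer that eligibility in this trial is actually decided after allocation; the documents permit that but do not establish it.

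Two further inferences should not be drawn. The imaging clause in section 4 concerns confirming the fracture, so it does not show that patients are randomised before the need for surgery is settled. The remark in section 5 that recruitment time "this may be longer depending on the number of patients who require definitive surgery" is an ordinary comment on the size of the eligible pool and says nothing about the order of decisions.

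It is also fair to object that unclear wording biases nothing unless patients are then removed, and that the illustration puts all the loss in one arm. Both points are accepted. They are why the withdrawal rule and the missing analysis population form part of this point.

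The charitable reading does not supply two things: any statement that acceptance precedes randomisation, and any protection for a randomised patient whose surgical plan changes.

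**Conclusion.** The point holds as an unresolved ambiguity with a route to bias. Section 4 and I. Design can be read as giving different entry rules, neither requires acceptance before randomisation, and section 10 allows removal on the strength of that ambiguity. Because both primary outcomes depend on surgery and no analysis population is defined, both would be exposed.

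The size in this trial cannot be computed. The complication shifts of about +2 to +5 or -3 to -6 percentage points, and the worst-case 0.20 to 0.35 SD for time to surgery, rest wholly on assumed inputs and one-sided removal. They show that the mechanism is not negligible and could run in either direction for complications. They do not show that it will occur. No sample-size figure changes.

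**What to change.** 1. In section 4, delete *eventually* and require that the surgeon's recommendation of definitive surgery and the patient's acceptance of it are both recorded before randomisation. Align I. Design with the same wording.
2. In sections 4 and 10, state that eligibility is judged once, on information available before randomisation, and that a later change of surgical plan is not a reason for withdrawal from the study or for replacement.
3. In IV. Analysis, state that all randomised patients are analysed by allocated arm, including those who never have definitive surgery. One way is to count time to surgery from randomisation and keep unoperated patients in the risk set, with soft tissue complications also counted from randomisation.

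The third step is needed because rewording entry alone still leaves an unoperated patient without a defined value for either primary outcome.

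The cost is mainly protocol wording. Some patients without an operative decision inside the 2-day window will not be enrolled; the documents do not show how many. Counting complications from randomisation also means recording them before surgery and in patients who have none, which the current visit schedule does not cover.
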